## 5. Strategy for Efficient Recruitment Strategies in Effects of Roflumilast in Hospitalized COPD on Mortality and Re-hospitalization

To ensure participation of a broad cross-section of patients and timely enrollment in this study, we will employ an aggressive and well-tested Temple recruitment strategy and we will collaborate with the other clinical centers. The Temple Lung Center has a strong record of clinical study recruitment and retention in the Philadelphia area, the greater Delaware Valley, throughout Pennsylvania, and from the entire mid-Atlantic region. Because we admit more AECOPD patients than any other hospital in Pennsylvania, we are especially well suited to serve as the recruitment anchor for the proposed study. We

currently maintain an IRB-approved clinical research registry with over 2500 COPD patients interested in clinical trials. Approximately one third of our COPD patients are black and over half are women. We have consistently succeeded in translating our high patient volumes and rich patient diversity into productive enrollment for national clinical trials. For COPD inpatient trials, potential research participants are identified during rounds on the pulmonary units, the emergency room, and on the pulmonary consult service. Internal medicine teams and case managers are contacted on a daily basis during the week. A listing of respiratory admissions is reviewed each day. Pulmonary section faculty members are regularly invited to local and regional meetings as well as hospital grand rounds where our research activities are showcased.

Because the proposed study seeks to enroll hospitalized COPD patients, we believe recruitment for this project will be challenging but achievable. This is why we propose a consortium of hospitals to achieve the recruitment endpoints. Temple Lung Center already has built a highly productive consortium of hospitals to participate in COPD trials such as the NHLBI long-term oxygen treatment trial (LOTT), simvastatin to prevent COPD exacerbations (STATCOPE), and our recently submitted NIH application for NIH RFP NHLBI-ECB-HR-2013-20-SS Engine for Fast Execution of Clinical Trials (EFFECT - Engine for Fast Execution of Clinical Trials). In both LOTT and STATCOPE, Temple leads recruitment of COPD subjects across all centers. In EFFECT, the planned focus is on hospitalized patients. For this study, we propose to use three of our consortium members from LOTT, STATSCOPE, and EFFECT.

Episcopal Campus for patients who require a short hospital stay. Full-time registered nurses and hospitalists staff this modern unit. If required, the Emergency Department or 21-bed inpatient telemetry unit can provide patients with fast access to specialized doctors and services at Temple University Hospital. All COPD patients seen at the Episcopal Campus who need inpatient care will be transferred as inpatients to Temple University Hospital Main Campus for their COPD hospitalization.

Appendix:

## **Biomarker Blood**

Biomarker specimens will be collected at baseline, every 6 months a participant is in the study, and at the last pre-washout visit.

## Preparation

1. Label all vacutainers and cryo-vials before the participant arrives. Use white labels for vacutainer tubes and colored cryo-labels for vials. Your sheet of white labels includes labels for the routine lab tubes and genetics tubes which you should also label at this time. It is recommended to assemble all the labeled tubes and vials in a large zip-lock bag with a white label on it to reduce errors.

2. Confirm that the participant has read, understood, and signed a consent form.

4. Determine whether the participant has ever had a bleeding disorder. If yes, check with the local study investigator regarding safety of proceeding.

Blood Collection and Processing

1. Blood samples will be collected in one 10 ml purple top K2EDTA tubes

2. Tubes should be promptly mixed after being drawn by gentle inversion 8-10 times (do not shake).

3. \*Centrifuge tubes at 1,100 RCF for 10 minutes.

\*Note: You need to put a small spacer at the bottom of the sleeve when centrifuging lavender top tubes. Don't use something that will get stuck in the sleeve or stuck on the tube (a cap from another tube, solid side up, has been suggested). The reason for the spacer is that the design of the lavender cap doesn't allow it to sit at the bottom of the sleeve and the force of the centrifuging will separate the tube from its top. Be sure that the centrifuge is balanced. Always have equivalent tubes opposite each other in order to

achieve the balance. If a tube does not have an equivalent tube use a similar type of tube filled with water to achieve the balance.

4. After centrifugation of the lavender top tube(s), carefully remove the hemogard. Using a plastic transfer pipette, and being careful not to disturb the red or white cell layers, transfer the clear plasma into lavender-labeled vials (1 ml in each vial). Note that 1 ml is about half the vial. It is imperative for analysis that the first tube of plasma be harvested from the very top of the plasma layer. You must aliquot sequentially. The last aliquot may be less than 1 ml (depending on what volume is remaining in the lavender top tube), but that aliquot should also be saved. Thus, the initial vials will contain 1 ml of plasma, the last vial may contain less than 1 ml, and some vials may remain empty and can be discarded. Never 'top off' the last vial as contents will expand and squeeze out the cap as they freeze. Always use a different pipette for every source tube. Remember that it's more important to get a pure sample than to get every last drop of plasma .

5. When filling vials, do not try to spread the contents equally across all available vials. Fill each vial to at least the 1 ml mark and put the remainder (< 1 ml) in the last vial. In most cases you will fill fewer vials than you have labeled.

6. If the plasma or serum has a slight pinkish color, hemolysis has occurred. Hemolysis results from the escape of hemoglobin from inside the red cells into the serum or plasma. Try to avoid the following things which cause hemolysis:

- Using too small a needle gauge
- Shaking the tubes
- Drawing blood from a hematoma
- Centrifuging the blood before it is completely clotted
- 7. The plasma must be isolated and aliquoted within 60 minutes of the draw.
- 8. Dispose of remaining blood products into red biohazard bag.

9. Seal cryo-vials firmly and place upright in tube rack or box. Place tube rack or box into -80°C freezer immediately. After the vials are frozen, the vials can be transferred into the participant's zip-lock bag awaiting shipment to the DCC. If it is more convenient for your lab, vials may remain in cell-divided freezer boxes for shipping to the DCC as long as vials remain in order by ID number and there is a separate packing list for each

ID. Boxes should be numbered (Box 1, Box 2, etc.) and the starting corner should be marked.

I. All vials should be in the -70°C freezer within 2 hours of phlebotomy.

Storage and Shipment of Vials

1. Vials should remain at -70°C until shipment.

## PAXGENE TUBES:

Obtain specimen in Pax Gene Tube Specimen remains at room temperature for for 2-2.5 hrs Freeze at -20 for 24 hours After 24 hours freeze at -70 until shipment

## Columbia Suicide Severity Rating Scale

The Columbia–Suicide Severity Rating Scale (C-SSRS) is a 2-page questionnaire that prospectively assesses suicidal ideation and behavior using a structured interview face to face for patient responses. Suicidal ideation is classified on a 5-item scale: 1 (wish to be dead), 2 (nonspecific active suicidal thoughts), 3 (active suicidal ideation with any methods [not plan] without intent to act), 4 (active suicidal ideation with some intent to act, without specific plan), and 5 (active suicidal ideation with specific plan and intent). The C-SSRS also captures information about the intensity of ideation, specifically the frequency, duration, controllability, deterrents, and reasons for the most severe types of ideation. Suicidal behavior is classified on a 5-item scale: 0 (no suicidal behavior),

1 (preparatory acts or behavior), 2 (aborted attempt), 3 (interrupted attempt), and

4 (actual attempt).

The C-SSRS will be performed during each evaluation visit according to the assessment schedule (see Figure 4). During visit, patients will complete the assessment with the health professional. Patients who do not have suicidal behavior or ideation will answer a limited number of questions and will usually complete the assessment in approximately 3 minutes. Patients with significant suicidal ideation and/or behavior may require up to 10 minutes to answer all relevant questions.

The patient should not be released from the evaluation site until it is confirmed

that the patient is not considered to be at any suicidal risk and all responses negative to the C-SSRS.

Positive reports are generated for any of the following findings:

- Suicidal ideation with intention to act (score of "4")
- Suicidal ideation with specific plan and intent (score of "5")
- Made suicide attempt
- Interrupted suicide attempt
- Aborted suicide attempt
- Preparatory behaviors for making a suicide attempt

At Screening (Visit 1), the C-SSRS will be completed for the patient's lifetime history

of suicidal ideation and behavior. At all other visits, the C-SSRS will be completed for

ideation and behavior since the previous visit. The patient's responses should remain negative throughout the entire trial. If a possible exclusion alert is triggered

by a positive response at Screening (Visit 1), 2 additional questions at the bottom of the

report will need to be asked to determine whether exclusion criteria 9a and/or 9b have

been met. A response of "Yes" to either one or both of the follow-up questions will exclude the patient from the trial and necessitate immediate psychiatric referral of the patient on the same date as the screening visit. For all subsequent visits after Screening (Visit 1), if the patient's response generates a change in the findings report from negative to positive, the patient should be referred for immediate psychiatric evaluation on the same date as the site visit and the PI will should be contacted. Positive suicidality indication findings reports after the Screening Visit (Visit 1), if confirmed by the *Investigator*, should be considered to be an AE. Ultimately, the determination of suicidality and risk is up to the *Investigator*'s clinical judgment.

Columbia – Suicide Severity Rating Scale Process

Forms:

Baseline/Screening Version

Since Last Visit Version

- Screening/Baseline Visit: Patient must not have a history of suicidal behavior ≤ 2 years or suicidal ideation ≤ 6 months prior to enrollment. The Screening/Baseline Version will be used to screen patients. During screening, if there is a positive response to questions 1 thru 5 do not enroll patient and notify the PI for possible psychiatric referral.
- 2. Clinic Visit 14 or Clinic Visit 180
  - During study patient's follow up clinic visit, the coordinator will assess for suicide risk utilizing the Since Last Visit version. A positive answer to question 4 or 5 indicating presence of ideation with at least some intent to die suggests a clear need for further evaluation or clinical management. Discuss with PI while patient still at visit C-SSRS score. Patient's scoring a 4 or a 5 should be discontinued from study and sent to Temple ER or to Episcopal ER for immediate evaluation.

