prospectively assesses suicidal ideation and behavior using a structured interview face to face for patient responses. The C-SSRS will be performed during each evaluation visit according to the assessment schedule on Figure 4. Suicidal ideation is classified on a 5-item scale: 1 (wish to be dead), 2 (nonspecific active suicidal thoughts), 3 (active suicidal ideation with any methods [not plan] without intent to act), 4 (active suicidal ideation with some intent to act, without specific plan), and 5 (active suicidal ideation with specific plan and intent). The C-SSRS also captures information about the intensity of ideation, specifically the frequency, duration, controllability, deterrents, and reasons for the most severe types of ideation. Suicidal behavior is classified on a 5-item scale: 0 (no suicidal behavior), 1 (preparatory acts or behavior), 2 (aborted attempt), 3 (interrupted attempt), and 4 (actual attempt). The C-SSRS will be performed during each evaluation visit according to the assessment schedule (see Figure 4). During visit, patients will complete the assessment with the health professional. Patients who do not have suicidal behavior or ideation will answer a limited number of questions and will usually complete the assessment in approximately 3 minutes. Patients with significant suicidal ideation and/or behavior may require up to 10 minutes to answer all relevant questions.

The patient should not be released from the evaluation site until it is confirmed

that the patient is not considered to be at any suicidal risk and all responses negative to the C-SSRS.

Positive reports are generated for any of the following findings:

- Suicidal ideation with intention to act (score of "4")
- Suicidal ideation with specific plan and intent (score of "5")
- Made suicide attempt
- Interrupted suicide attempt
- Aborted suicide attempt
- Preparatory behaviors for making a suicide attempt

At Screening (Visit 1), the C-SSRS will be completed for the patient's lifetime history

of suicidal ideation and behavior. At all other visits, the C-SSRS will be completed for Version 04.13.2015

ideation and behavior since the previous visit. The patient's responses should remain negative throughout the entire trial. If a possible exclusion alert is triggered

by a positive response at Screening (Visit 1), 2 additional questions at the bottom of the

report will need to be asked to determine whether exclusion criteria 9a and/or 9b have

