been met. A response of "Yes" to either one or both of the follow-up questions will exclude the patient from the trial and necessitate immediate psychiatric referral of the patient on the same date as the screening visit. For all subsequent visits after Screening (Visit 1), if the patient's response generates a change in the findings report from negative to positive, the patient should be referred for immediate psychiatric evaluation on the same date as the site visit and the PI will should be contacted. Positive suicidality indication findings reports after the Screening Visit (Visit 1), if confirmed by the *Investigator*, should be considered to be an AE. SAEs must be *reported* as outlined in Section 6. Ultimately, the determination of suicidality and risk is up to the *Investigator*'s clinical judgment.

**4. I. Measurements of Dyspnea.** Dyspnea will be measured by use of the modified Medical Research Council Dyspnea score. This is a well-known, validated and easy to use scale that is a reliable and sensitive tool specific to COPD patients that will allow detection of a response to therapy as well as comparison to other studies reporting dyspnea as an outcome in other COPD trials.

**4.** J. Description of Optimized Standard Care for COPD Exacerbations. All patients will receive standardized, optimized care for AECOPD {{387 Niewoehner,D.E. 1999}}. Nebulized albuterol (2.5 mg in 0.5 ml, dilute to 3 ml NSS administered every 4-6 hours) and ipratropium bromide (0.5 mg in 0.5 ml, diluted with 2.5 ml of saline administered every 6 hours) will be given. A 14-day course of systemic steroids consisting of intravenous methylprednisolone 125 mg every 6 hours for up to 72 hours, followed by once daily oral prednisone 60mg/day for days 4-7, 40 mg prednisone days 8-11 and 20 mg prednisone days 12-14 will be provided. A 7-day course of antibiotics will be selected based on patient's medical allergy history and relevant culture data if available. Supplemental oxygen will be provided by route and dose to achieve maximum patient comfort and compliance to maintain a  $SaO_2 > 92\%$ . Noninvasive positive pressure ventilation will be utilized at the discretion of the treating physicians but will follow accepted guidelines {{133 Keenan,S.P. 2003; 136 Lightowler,J.V. 2003}}.

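### The only mandatory C-SSRS stopping rule is tied to ideation 4 or 5, so suicidal behaviour reported at day 14 has no stop-drug trigger

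*Combined protocol and SAP*

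**What the plan says.** Section 4.H and the appendix on the Columbia Suicide Severity Rating Scale give the same list of findings that generate a positive report. Two are ideation scores (4 and 5). Four are behaviours: an actual attempt, an interrupted attempt, an aborted attempt and, last on the list, "Preparatory behaviors for making a suicide attempt".

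For any change from negative to positive after screening, both places require that "the patient should be referred for immediate psychiatric evaluation on the same date as the site visit", and that the principal investigator be contacted. A positive finding that the investigator confirms is recorded as an adverse event. Both also contain a hold rule: "The patient should not be released from the evaluation site until it is confirmed" that there is no suicidal risk and that all responses are negative. The final determination of risk is left to the investigator's clinical judgment.

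The only text that takes a patient off anything is item 2 of the C-SSRS Process in the appendix, which covers the day 14 and day 180 clinic visits. It opens its action text with "A positive answer to question 4 or 5 indicating presence of ideation with at least some intent to die", and ends with "Patient's scoring a 4 or a 5 should be discontinued from study and sent to Temple ER or to Episcopal ER for immediate evaluation".

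For screening, item 1 first restates the two exclusion windows of section 4.A (behaviour within 2 years, ideation within 6 months). It then says that "if there is a positive response to questions 1 thru 5 do not enroll patient and notify the PI for possible psychiatric referral".

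**The concern.** The plan's definition of a positive finding and its stopping rule do not cover the same patients. Intent to act without a plan (ideation 4) forces discontinuation and an emergency-room visit. An interrupted or aborted attempt, reported without ideation 4 or 5, forces neither, although the plan classes both as positive.

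Section 4.N records that roflumilast carries a warning for psychiatric events and suicidality. A mandatory stop was evidently thought right for serious ideation, and no reason is given for leaving reported behaviour to discretion. At stake is whether such a patient continues a drug with that warning under a rule or under case-by-case judgment.

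The existing rule also removes the patient from the study rather than from the drug. That fits poorly with an intention-to-treat analysis of a 180-day endpoint.

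**Working it through.** The plan gives no figure to reproduce here. The check is to set the rules side by side and see which findings each one reaches.

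**1. Actions at a clinic visit after screening.** Inputs: the positive-findings list, hold rule and referral rule (section 4.H and appendix), and C-SSRS Process item 2 (appendix). Behaviour is scored separately from ideation, from 0 (none) to 4 (actual attempt).

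| Finding | Hold, same-day psychiatric evaluation, PI contact | Mandatory discontinuation and ER |
|---|---|---|
| Ideation 5 | yes | yes |
| Ideation 4 | yes | yes |
| Actual attempt (behaviour 4) | yes | no on the natural reading; yes on a loose one |
| Interrupted attempt (behaviour 3) | yes | no |
| Aborted attempt (behaviour 2) | yes | no |
| Preparatory behaviour (behaviour 1) | yes | no |

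2 ideation + 4 behaviour = 6 positive findings. Item 2 reaches 2 on the natural reading, leaving 6 − 2 = 4 without a stop trigger. If a score of 4 is also taken to include behaviour score 4, it reaches 3, leaving 6 − 3 = 3. These are counts of list items, not of risk.

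**2. When the gap can change drug exposure.** Section 4.B sets 180 days of treatment and lists the C-SSRS after baseline only at days 14 and 180; item 2 names the same two visits. At day 180 the planned dosing left is 180 − 180 = 0 days, so a stop rule has nothing to act on. The gap therefore matters at day 14.

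**3. Other stopping rules.** Section 4.H has none. Section 4.P says only that adverse events are still collected from subjects permanently off drug who remain in outcome follow-up. Section 4.R says only when follow-up is censored. The appendix management table is graded by ideation level and contains no instruction on study drug.

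**4. Removal from study versus removal from drug.** Section 4.P already provides for patients off drug but still followed. Section 4.R analyses everyone as randomised, whether or not they adhered, and lists three censoring events: loss to follow-up, withdrawal of consent, and day 180. Removal by the investigator is not among them. If item 2 is followed literally, the plan does not say how that patient's follow-up enters the log-rank test.

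**5. Screening wording.** At screening, "the C-SSRS will be completed for the patient's lifetime history". Section 4.H and the appendix then exclude through two follow-up questions: a yes "to either one or both of the follow-up questions will exclude the patient from the trial". The last sentence of item 1 names neither a window nor those questions. Read literally against a lifetime form, it could bar a patient whose only ideation was more than 6 months ago, whom section 4.A would admit. Read within the windows stated just before it, it does not. This is an ambiguity, not a contradiction.

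**The case against.** The strongest reply is that acute safety is already handled. Every behaviour on the list triggers the hold, the same-day evaluation and contact with the principal investigator, and the investigator may stop the drug. This stands. A reader might infer that the plan leaves a patient who reports an attempt unmanaged, and the documents do not support that. Same-day psychiatric evaluation also differs little from an emergency-room visit. What remains is that stopping is mandatory for serious ideation and discretionary for behaviour.

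Second, the operative sentence does not contain the word ideation, and an actual attempt is scored 4 on the behaviour scale. A coordinator might apply the rule to it. The ideation reading is more natural because the same item defines its trigger that way, but the looser one cannot be excluded. Even so, three behaviours stay uncovered.

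Three further inferences are tempting and should not be drawn:

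- **Long continued dosing.** After day 14, 180 − 14 = 166 planned dosing days remain. Nothing directs that dosing continue after a positive finding, a hold and a psychiatric evaluation, and the phone visits collect adverse events and ask about tolerance. The 166 days are not a measure of the harm.
- **Routine referral for behaviour.** The management table would suggest this only if read alone. It is headed as an ideation table, it follows the same-day rule in the same appendix, and nothing says it overrides that rule.
- **Conflicting referral rules at screening.** Item 1 speaks of possible referral after any positive answer to questions 1 to 5. The mandatory same-day referral follows a yes to a follow-up question. The triggers differ, so the two texts do not conflict.

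Finally, it can be said that the plan intends investigator confirmation before acting. It asks for confirmation before recording an adverse event. Item 2 asks for discussion with the principal investigator while the patient is still at the visit, but does not make the stop for ideation 4 or 5 wait for confirmation. Extending the trigger keeps the same pattern.

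**Conclusion.** The narrow point holds: item 2's mandatory stop does not reach at least three, and on the natural reading four, of the six findings that the plan itself calls positive. It is an omission, not an instruction to continue treatment. It bears on drug exposure at one scheduled visit in a pilot of about 100 patients whose entry criteria already exclude recent suicidal behaviour. The documents give no rate for such behaviour, so no number of affected patients can be stated. No endpoint definition, sample size or analysis figure is affected.

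This is a cheap improvement in patient safety, of minor severity. The screening wording is a secondary clarification.

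The conclusion assumes that Figure 4 (the assessment schedule) and the C-SSRS forms, which are not available, contain no separate stopping rule, and that the visit text gives the C-SSRS schedule correctly.

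**What to change.** 1. In C-SSRS Process item 2, make the trigger any of the six positive findings, with this action: stop study drug, send for immediate emergency evaluation, and continue outcome follow-up to day 180. This replaces removal from the study and agrees with sections 4.P and 4.R.
2. As a clarification, state that the last sentence of item 1 applies within the 6-month ideation and 2-year behaviour windows of section 4.A, as decided by the two follow-up questions.

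The cost is a few lines of wording in the appendix and a reissued coordinator worksheet, with no new assessments. The downside is possibly a few more study-drug discontinuations. Continued follow-up keeps those patients' 180-day outcomes in the intention-to-treat analysis.

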## 4. P. Assessment of Safety

#### 1. Definition of adverse event.

An adverse event is any untoward medical experience occurring in a subject doing the trial whether or not is related to study drug. An adverse event includes a concurrent illness, injury, or any other aspect of the subject's health, as well as abnormal laboratory findings found to be of clinical significance. An adverse event includes worsening of an existing symptom or condition or post treatment events that occur as a result of protocol – mandated procedures.

An adverse event may be a disease, a set of related symptoms or signs, or single symptom or sign including an abnormal laboratory value.

For the purposes of this trial, all adverse events will be collected including adverse events that occurred subjects were permanently off of study drug but who continue to be followed for outcomes.

A serious adverse event is an adverse event occurring any does that results in any of the following, whether or not it is related to study drug: death, immediately life-

threatening circumstance, inpatient hospitalization or prolongation of existing hospitalization, a persistent or significant disability.

Life-threatening means that the subject in the view of the investigator was thought to be at immediate risk of death from the event as it occurred.

Serious events will be collected, including serious adverse events occurring when subjects were permanently off study drug but who continue to be follow-up for outcomes.

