## 4. R. Statistical analysis plan.

The primary analysis for all study outcomes will be performed on an intention to treat basis. In the intention to treat approach, all subjects are analyzed in the group to which they were randomized, regardless of whether the assigned treatment was adhered to and regardless of whether there were any eligibility violations.

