## 1. Analysis of baseline characteristics.

Univariate descriptive statistics will be calculated for baseline parameters overall and by treatment group. For categorical outcomes, these will include the number percentage of subjects in each category. For continuous variables, these will include the mean and standard deviation for variables with approximately normal distributions and the median and 25th and 75% percentiles for variables with skewed distributions.

**2.** Analysis of the primary endpoint. The primary outcome is time from randomization to a composite outcome of all cause re-hospitalization and all-cause mortality, whichever comes first. The primary analysis will be a log-ranked test and associated Kaplan-Meier plot, unadjusted for any covariates. Censoring will occur at the earliest date of any of the following occurrences, unless the subject has already experienced the primary outcome event:

• Lost to follow-up despite intensive efforts

- Subject or healthcare proxy withdrawal of consent
- 180 days after randomization.

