#### MANAGEMENT PROTOCOL

Level	Severity	
0	Low Risk	ROUTINE Behavioral Health Referral at physician discretion
1 & 2	Mild	ROUTINE Behavioral Health Referral at physician discretion
3	Moderate	Review by physician—Consider safety precautions and telephone consult with Behavioral Health
4 & 5	Serious	EMERGENT ACTION NECESSARY: Behavioral Health Consultation and Patient Safety Monitor/Procedures

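### The appendix takes patients with a C-SSRS score of 4 or 5 off the study rather than off study drug; read literally at day 14, that ends up to 166 of 180 days of outcome follow-up

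*Combined protocol and SAP*

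**What the plan says.** The C-SSRS process in the appendix covers the day 14 and day 180 clinic visits. It tells the coordinator: "Discuss with PI while patient still at visit C-SSRS score". The next sentence says that patients "scoring a 4 or a 5 should be discontinued from study and sent to Temple ER or to Episcopal ER for immediate evaluation". It does not mention study drug, later calls or visits, or how the patient's data are handled.

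Other parts of the document bear on the same patient:

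- **Section 4.H**, repeated in the appendix, covers a report that turns positive after screening: "the patient should be referred for immediate psychiatric evaluation on the same date as the site visit". The principal investigator is contacted and a confirmed finding is an adverse event. Discontinuation is not mentioned.
- **The management table** at the end of the appendix asks, for ideation levels 4 and 5: "EMERGENT ACTION NECESSARY: Behavioral Health Consultation and Patient Safety Monitor/Procedures". Discontinuation is not mentioned here either.
- **Section 4.P.1** collects adverse events in subjects "permanently off of study drug but who continue to be followed for outcomes", with a parallel sentence for serious events.
- **Section 4.R** analyses everyone as randomized, "regardless of whether the assigned treatment was adhered to".
- **Section 4.R.2** introduces its censoring rule with "Censoring will occur at the earliest date of any of the following occurrences". It lists three reasons: loss to follow-up despite intensive efforts, "Subject or healthcare proxy withdrawal of consent", and day 180.

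**The concern.** The protocol distinguishes elsewhere between being off drug and being out of follow-up, but this sentence does not. A coordinator who applies it as written at day 14 would make no further scheduled contact. Re-hospitalizations and deaths after that date, and the day 180 SGRQ, EQ-5D, MMRC and spirometry, would then have no planned collection. The patient would not have withdrawn consent, and calling them lost despite intensive efforts would be untrue, so no early censoring reason in section 4.R.2 fits.

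The reason for removal also matters. Section 4.N reports a warning for psychiatric events and suicidality with roflumilast. If removals were more frequent on active drug, the missing follow-up would depend on arm and could be informative, in a pilot whose first aim in section 4.Q is tolerance. These are also patients for whom the study's continued contact has safety value.

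**Working it through.** **1. The plan's own design figure.** Section 4.R.4 gives a hazard ratio of 1.654, two-sided alpha 0.10, power 0.70 and 73 events. Schoenfeld's formula with 1:1 allocation (assumed) gives

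events = 4 × (1.645 + 0.524)² / (ln 1.654)² = 74.3, or 75 when rounded up.

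Power at 73 events is 0.693. The stated figure is reproduced to within two events.

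**2. Follow-up lost by one patient.**

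- Removed at day 14: 180 − 14 = 166 days, and 166/180 = 92%. This is a maximum, because a patient who has already had a primary event loses no primary-outcome time. The contacts lost are the calls at days 30, 60, 90, 120 and 194 and the day 180 visit: five calls and one visit.
- Removed at day 180: no primary follow-up is lost, only the day 194 call.

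**3. Chance that a lost patient would have had an event.** Assume exponential times, 30.44 days per month and the plan's 8-month median. The other arm's median is 8 × 1.654 = 13.2 months or 8 / 1.654 = 4.8 months, depending on which arm the 8 months describes. For a patient event-free at day 14, with 166 days = 5.45 months left:

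P = 1 − exp(−ln 2 × 5.45 / median)

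| Median (months) | P(event, day 14 to 180) | Expected loss, 1 removal | Expected loss, 2 removals |
|---|---|---|---|
| 13.2 | 0.25 | 0.25 | 0.50 |
| 8 | 0.38 | 0.38 | 0.75 |
| 4.8 | 0.54 | 0.54 | 1.08 |

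The number of removals is an assumption. The documents give no rate of scores of 4 or 5. I take 0 to 2 of 100 patients at day 14; zero is plausible because recent ideation and behavior are screened out.

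**4. Events expected by day 180.** With 50 patients per arm and 180 days = 5.91 months, the event probabilities are 0.401 (median 8), 0.266 (13.2) and 0.572 (4.8).

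- Medians 8 and 13.2: 20.05 + 13.32 = 33.4 events.
- Medians 8 and 4.8: 20.05 + 28.58 = 48.6 events.

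I use these rather than 73, because section 4.R.2 censors at day 180.

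**5. Effect on power.** Power = Φ(ln 1.654 × √D / 2 − 1.645), where D is the number of events.

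| Events by day 180 | No removal | 1 removal (−0.38) | 2 removals (−0.75) |
|---|---|---|---|
| 33.4 | 0.424 | 0.421 | 0.418 |
| 48.6 | 0.544 | 0.541 | 0.538 |

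One removal costs 0.8 to 1.1% of events and about 0.3 percentage points of power. Two cost 1.5 to 2.2% of events and 0.5 to 0.7 points. At the top of the range, losing 1.08 of 48.6 events lowers power from 0.544 to 0.536, or 0.8 points. On the plan's 73 events, losing 0.75 lowers power from 0.693 to 0.689.

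**6. What this does not measure.** Steps 3 to 5 measure lost information. They say nothing about bias, which would need the rate of such scores by arm and its relation to later events. The documents give neither.

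**The case against.** The case against is that this is loose wording in a safety procedure and the governing text already settles the matter. Much of that stands. Section 4.R.2 gives a closed list of censoring reasons without a C-SSRS score, section 4.R is intention to treat, and section 4.P.1 foresees off-drug follow-up. The appendix may well mean study drug. It asks for discussion with the principal investigator first, and it leaves the judgment of risk to the investigator.

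There is also a second route for data. Every inpatient admission or death is a serious adverse event, reportable within 24 hours, and serious events are followed to resolution, stabilization, death or withdrawal. An admission arising from the ER referral would probably be known, and it already counts as a primary event because section 4.R.2 includes re-hospitalization from any cause. That route weakens for later events if staff take the literal reading, since the scheduled contacts would have stopped.

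A reader might infer that the appendix orders staff to stop follow-up, in direct contradiction of the main text. The documents do not support that: the sentence does not mention calls, vital status or censoring, so it is ambiguous rather than opposite. A reader might also infer that the primary comparison will be biased. Section 4.N gives a warning but no suicidality rate by arm, so arm-related loss is only a possibility.

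What remains is that no sentence tells site staff to keep following these particular patients, and the one operational instruction they have can be read as telling them not to.

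**Conclusion.** The point holds as a minor inconsistency. Read literally at day 14, the sentence ends scheduled outcome and safety follow-up for that patient and conflicts with sections 4.P.1, 4.R and 4.R.2. The 166 days is a maximum for one patient, not a trial-level effect. With no removals nothing is lost; with two, the loss is below about one percentage point of power. Those figures rest on an assumed 0 to 2 removals, exponential event times, the 8-month median and 50 patients per arm. The reasons to correct it are consistency, a possible but unquantified bias, and keeping high-risk patients in contact with the study.

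**What to change.** In the appendix sentence, limit the discontinuation to study drug, keep the emergency referral as it stands, and add wording such as: *all scheduled follow-up (phone calls; the day 180 visit with SGRQ, EQ-5D, MMRC and spirometry; vital status, re-hospitalization and adverse events) continues to day 194 unless consent is withdrawn.* Naming the day 180 measures matters, because a clause limited to vital status, re-hospitalization and adverse events would not recover them.

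The score at which drug is stopped stays with the sponsor.

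The cost is one amended sentence and, for each rare patient, at most five calls and one clinic visit, all already scheduled.
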